7.0 RECRUITMENT PLAN

The study will be conducted at Memorial Sloan Kettering Cancer Center. Patients will be treated by the lymphoma service at MSKCC. Every effort will be made to include women and minorities in this research study. Patients will be recruited by the treating team of physicians and medical professionals. The consenting attending physician will inform patients of their diagnosis, current treatment options, including standard treatment, and the risks, benefits, and experimental nature of this treatment program. All patients will be required to sign a statement of informed consent that conforms to FDA and IRB guidelines.

8.1 PRETREATMENT EVALUATION

Prior to initiating treatment:

- Prior biopsy with pathologic confirmation of MCL.
- Archival block 10-15 x 10 micron unstained slides and 1 H&E will be requested. A minimum of 40 micron material is requested.
- If archival tissue is not available, patients will be asked to provide informed consent for an optional repeat biopsy.

Within 4 weeks prior to initiating treatment:

- Medical history and demographics
- Complete history and physical exam (including weight, pulse, blood pressure, temperature, ECOG performance status)
- Medication review
- Hepatitis B surface antigen and Hepatitis B core antibody (HBV DNA PCR is only required if HBsAg is positive)
- Hepatitis C antibody
- HIV testing
- Cytomegalovirus PCR testing
- ECG
- Echocardiogram or MUGA to evaluate cardiac function
- PET scan
- CT chest/abdomen/pelvis and neck CT if clinically indicated (MRI will be used for those who are unable to undergo CT scans).

Within 1 week prior to initiating treatment:

- Blood work: CBC with differential, PT/INR, electrolytes (Na, K, Cl, CO2), BUN, Cr, total bilirubin, total protein, albumin, AST, ALT, alkaline phosphatase, uric acid, LDH, magnesium, phosphorus, lipid panel, thyroid function tests, hemoglobin A1c, fructosamine, amylase, lipase, urinalysis, GFR
- Serum beta-HCG (for WOCBP only) to assess for pregnancy

[figure not shown]

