- Patient has a concurrent active malignancy. Malignancies treated with a curative intent with an expected life expectancy \geq 5 years or a non-competing life expectancy risk are eligible (i.e. adequately treated basal or squamous cell carcinoma, non-melanomatous skin cancer, early stage breast cancer, treated prostate cancer or any other cancer from which the patient has been disease free for \geq 3 years).
- Patient with known history of human immunodeficiency virus (HIV), or any uncontrolled active systemic infection.
- Patient has CMV viremia (peripheral blood CMV PCR positive), acute viral hepatitis (typically defined by elevated AST/ALT), or a history of chronic or active HBV or HCV infection. HBV infection is defined as having HBsAg and/or HBcAb positive test with concurrent detectable HBV DNA levels. HCV infection is defined as detectable HCV RNA levels.
- Patient requires treatment with a strong or moderate cytochrome P450 (CYP) 3A4 inhibitors, and inducers, and the treatment cannot be discontinued or switched to a different medication prior to starting study drug. Moderate and strong CYP modulators (inducers and inhibitors) should have a washout period of at least 5-6 half-lives before initiating ibrutinib or copanlisib.
- Patients with known bleeding diathesis (e.g. von Willebrand 's disease) or hemophilia
- Patient is currently receiving warfarin or other Vitamin K antagonist. Therapy with heparin, low molecular weight heparin (LMWH), or fondaparinux is allowed. Refer to Section 9.5 for Concomitant medication
- Patients with Child Pugh Class B or C hepatic cirrhosis
- Patients with any life threatening illness, medical condition or organ system dysfunction that in the opinion of the investigator could compromise the subject's safety, interfere with absorption of metabolism of study drugs or put the study outcomes at undue risk.

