T3, T4, TSH		X				As clinically indicated			X
Fructosamine		X			X	X			X
Hemoglobin A1c		X				X			X
Coagulation (PT/PTT)		X							X
B cell Clonality by NGS			X			Day 1 Cycle 3, 5, 7, 10, 13, 17, 21, 25, 29, 33			X
Hepatitis B/C ^B	X					Hepatotoxicity testing/procedures as clinically indicated ^C			
HIV	X								
Cytomegalovirus PCR	X					X			X
Serum/Urine beta-HCG for women of childbearing age		X							
Post Infusion Glucose Evaluation ^D			X ^D Fasting	X ^D	X ^D	X ^D	X ^D		
Post Infusion Blood Pressure ^E			X ^E	X ^E	X ^E	X ^E	X ^E		
Radiographic assessment ^F	X					Before Day 1 Cycle 3, 5, 7 (first 6 months), 10, 13, (1 year), 17, 21, 25, 31 (year 2-3)		X (if not within 4 weeks)	
ECHO or MUGA	X							X	
ECG	X							X	

PCP pneumonia prophylaxis			Continuous (unless clinically contraindicated)				
Pill Diary			X		X		X
Tumor biopsy(archived/fresh biopsy) ^G	X ^G				Optional ^G		
Research Blood Tests: ctDNA, ctRNA		X	X	X	Cycle 2: D1, D8, D15 Cycle 3-7: D1	X	
Research Blood Tests: Pharmacokinetics ^J				X			

A: Copanlisib Dosing: If copanlisib is held based on achievement of a complete response, patient visits will be every 2 cycles during C1-C6, every 3 cycles during C7-C12, every 4 cycles during C13-36.
B: Hepatitis Evaluation: HbsAg, HBcAb, anti-HCV Ab, Hep B/C PCR if positive
C: Additional viral hepatitis workup as clinically warranted: HAAb, HBsAg, HBsAb, HBcAb, HCV RNA or HDV RNA (where needed), H EAb, CMVAb, EBcAb, CMV IgM Ab, EBV IgM Ab, HSV, AP, CPK, LDH, Carriers of hepatitis B should be closely monitored for clinical and laboratory signs of active HBV infection, signs of hepatitis during and for several months following ibrutinib/copanlisib treatment. Carriers of hepatitis B (positive HBsAg and/or HBcAg but negative HBV-DNA is required to be on prophylactic antiviral therapy. If viral load becomes positive, patients should be withdrawn from study. Hep C carriers (anti-HCV Ab positive, negative HCV-RNA PCR must be tested monthly for HCV reactivation. If HCV-RNA PCR becomes positive, patients should be withdrawn from study.
D: Post Infusion Glucose Evaluation: C1D1 – fasting glucose prior to copanlisib (0h), 60 min (end of infusion) and 2 hours; all subsequent doses – non-fasting glucose prior to copanlisib (0h), post infusion.

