14.2. Phase II

The primary objective for this phase II cohort is to assess the complete response rate based on best response by 6 months of ibrutinib and copanlisib and the secondary objective is to measure the disease control rate (stable disease, partial response, and complete response), overall response rate (partial and complete response), duration of response, progression and event free survival. A Simon mini-max two stage design will be used with the goal to increase by complete response rate based on best response by 6 months from 20% to 40%. In first stage, if 5 or more of 18 patients have responses, then the trial will proceed to stage 2. In stage 2, additional patients are enrolled to make the total sample size 33. If 11 or more responses are observed, then the combination is deemed promising. Accrual will not be held while the initial 18 patients in the first stage are evaluated for the 6-month response endpoint. The one sided type I error rate is 0.05 and the power is 0.80. A total of 33 patients will be enrolled, though patients treated at MTD/RP2D from phase I portion of the study will be included in the phase II analysis. Expected accrual is 2-3 patients per month and so the phase II portion will be completed within a year.

For other secondary objectives, the event free survival and progression free survival rates will be assessed by the Kaplan-Meier estimation. Event free survival is defined from the date of first dose to progression, or death, and any events including treatment discontinuation for adverse events or severe adverse events whichever came first. Progression free survival is defined from the date of first dose to progression or death, whichever came first. The duration of response will also be assessed by Kaplan-Meier method but on a sub-cohort of patients who showed any response.

To protect patients from excessive toxicity of the treatment during the entire treatment period, several stopping rules are implemented during the study based on the maximum total number of treated patients in both phase I and II (45). **Treatment related Grade ≥ 3 Pneumonitis or Colitis:** 10% unacceptable rate, 2.5% acceptable rate. Trial to hold enrollment if ≥ 4 deaths related to treatment at any point during the study. Otherwise, hold enrollment based on number of treated patients.

Number of treated patients	1	14	33	45
Number of Gr ≥ 3 Pneumonitis/Colitis to stop the trial	1	2	3	4

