15.1 RESEARCH PARTICIPANT REGISTRATION AND RANDOMIZATION PROCEDURES

15.2 Research Participant Registration

Confirm eligibility as defined in the section entitled Inclusion/Exclusion Criteria. Obtain informed consent, by following procedures defined in section entitled Informed Consent Procedures. During the registration process registering individuals will be required to complete a protocol specific Eligibility Checklist. The individual signing the Eligibility Checklist is confirming whether or not the participant is eligible to enroll in the study. Study staff are responsible for ensuring that all institutional requirements necessary to enroll a participant to the study have been completed. See related Clinical Research Policy and Procedure #401 (Protocol Participant Registration).

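### Section 8.1 asks for HBV DNA only when HBsAg is positive, so the Section 6.3 hepatitis B exclusion cannot be decided for HBsAg-negative, HBcAb-positive patients.

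*Combined protocol and SAP*

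**What the plan says.** Section 8.1 orders both HBsAg and HBcAb for every patient within 4 weeks before treatment, and adds: "HBV DNA PCR is only required if HBsAg is positive".

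Section 6.3 excludes chronic or active hepatitis B and defines it so: "HBV infection is defined as having HBsAg and/or HBcAb positive test with concurrent detectable HBV DNA levels".

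In Table 10-1, the Hepatitis B/C row is marked at screening and carries footnote B: "HbsAg, HBcAb, anti-HCV Ab, Hep B/C PCR if positive". After screening, the same row gives no fixed schedule: "Hepatotoxicity testing/procedures as clinically indicated".

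Footnote C of that table covers carriers. For hepatitis B it says "positive HBsAg and/or HBcAg but negative HBV-DNA is required to be on prophylactic antiviral therapy", asks for close monitoring, and requires withdrawal if the viral load turns positive. It gives no interval for repeat HBV DNA. Hepatitis C carriers, by contrast, "must be tested monthly for HCV reactivation".

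Section 15.2 makes one person answerable for eligibility: "The individual signing the Eligibility Checklist is confirming whether or not the participant is eligible to enroll in the study".

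**The concern.** Section 8.1 requires the core antibody in everyone but attaches no DNA test to an isolated positive result. That is a pattern the and/or in Section 6.3 covers, and only a DNA result can settle the exclusion for it. A site working from Section 8.1 could therefore enroll and treat a patient who meets the hepatitis B exclusion without departing from the Section 8.1 test list. The checklist signer would be confirming an exclusion that nobody had assessed.

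The omission also affects later decisions. The withdrawal rule in footnote C and the removal criterion in Section 13 for active HBV both describe a change during the study. Without a baseline DNA result, viremia present at entry cannot be told from reactivation on treatment. If the core marker printed in footnote C as HBcAg is meant to be HBcAb, the prophylaxis rule for DNA-negative carriers needs the same missing result. That reading is an inference.

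**Working it through.** **Step 1: compare the texts by serology pattern.**

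| HBsAg | HBcAb | DNA needed for Section 6.3? | Required by Section 8.1? | Required by footnote B? | Consistent? |
|---|---|---|---|---|---|
| + | + or − | Yes | Yes | Yes | Yes |
| − | − | No | No | No | Yes |
| − | + | Yes | **No** | Yes, on its natural reading | **No** |

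Footnote B does not name the marker that triggers PCR. Its condition follows a list that includes HBcAb and does not limit it to HBsAg. Section 8.1 does limit it, through the word *only*. Section 8.1 is therefore the outlier, and the conflict is confined to the third row.

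**Step 2: look for a later test that would recover the baseline.** None is scheduled. After screening, hepatitis testing is done on clinical indication, and footnote C sets no HBV DNA interval.

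**Step 3: size.** The plan gives no figure to reproduce on this point. The only input from the documents is the maximum number treated. Phase I allows 18 patients, phase II has 33, and 6 are counted in both (Section 4.2, Table 9-3): 18 + 33 − 6 = 45, which agrees with Section 14.2.

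Two inputs are assumptions, because the documents give neither:
- *p*, the proportion of patients who are HBsAg-negative and HBcAb-positive: 1% to 10%.
- *d*, the share of those with detectable HBV DNA: 1% to 100%.

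Everything below is conditional on staff following Section 8.1 rather than footnote B.

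| *p* | Expected with undetermined status, 45 × *p* | Chance of at least one, 1 − (1 − *p*)^45 |
|---|---|---|
| 1% | 0.45 | 1 − 0.99^45 = 0.364 |
| 5% | 2.25 | 1 − 0.95^45 = 0.901 |
| 10% | 4.5 | 1 − 0.90^45 = 0.991 |

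The expected number wrongly enrolled is 45 × *p* × *d*:
- lowest: 45 × 0.01 × 0.01 = 0.0045
- middle: 45 × 0.05 × 0.10 = 0.225
- highest: 45 × 0.10 × 1.00 = 4.5

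The chance of at least one in the first table refers to a patient whose status is undetermined, not to one wrongly enrolled.

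**The case against.** The strongest reply is that the texts can be satisfied together. Section 8.1 does not forbid the PCR, so a site that honors every section would run it. Section 8.1 is also plainly not self-sufficient on hepatitis: it lists the hepatitis C antibody but no HCV RNA, although Section 6.3 defines HCV infection by RNA, so footnote B has to supply that follow-on test. Enrolling a DNA-positive patient would still breach Section 6.3, and the checklist is a point at which the gap could be noticed. There are partial safeguards as well: transaminase limits at entry (Section 6.2), repeated chemistry on treatment (Table 10-1), and withdrawal for a positive viral load or active HBV (footnote C, Section 13). Finally, the size rests wholly on assumed inputs and spans a thousandfold range.

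Much of this is fair, and it limits the consequence. It does not remove the conflict. For HCV, Section 8.1 is silent and footnote B fills the gap; for HBV, Section 8.1 states a narrower trigger, and the plan gives no rule on which text prevails. Section 6.3 lists HBV infection separately from acute hepatitis marked by raised transaminases, so normal enzymes do not stand in for a DNA result. None of the later safeguards supplies a baseline. The objection on size stands in that the figures show a range and are not an estimate. The absence of an HBV DNA monitoring interval is a separate matter that the change below does not address.

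**Conclusion.** The inconsistency is real and follows from the text alone. For HBsAg-negative, HBcAb-positive patients, Section 8.1 does not require the result on which the Section 6.3 exclusion depends and for which footnote B, naturally read, calls. For HBsAg-positive patients there is no gap.

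If staff follow Section 8.1, and with an assumed prevalence of 1% to 10%, 0.45 to 4.5 of 45 treated patients would have undetermined exclusion status, and the chance of at least one is 36% to 99%. Between 0.0045 and 4.5 would be wrongly enrolled, the upper figure being reached only if every such patient had detectable DNA. If staff follow footnote B, the exclusion can be applied and these numbers do not arise.

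This is a patient-safety and eligibility point that should be corrected. It has no bearing on error rates, sample size, stopping rules or the primary analysis.

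**What to change.** Let Section 6.3 govern. Reword Section 8.1 to read: *HBV DNA PCR is required if HBsAg or HBcAb is positive.* State the same trigger explicitly in footnote B of Table 10-1. In footnote C, correct HBcAg to HBcAb if that is what is meant.

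The cost is one line in Section 8.1 and matching wording in two footnotes. Under the assumed 1% to 10% prevalence, it adds about 0.45 to 4.5 HBV DNA tests per 45 patients tested. The total would be somewhat higher if more patients are screened than treated; the number screened is not given. The test is one that footnote B already lists.

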9.0 TREATMENT/INTERVENTION PLAN

9.1. Study Treatment

The investigational agents to be used in this study are copanlisib and ibrutinib. Copanlisib is given intravenously on days 1, 8, and 15 of 28 day cycles. Ibrutinib is given orally every day on 28 days cycles. The maximum duration of treatment is 36 cycles not exceeding 36 months. Dose changes or interruptions are allowed per below guidelines and must be recorded appropriately.

Study personnel will maintain a log of all drugs supplied to the patient. Drug supplies for each patient will be inventoried and accounted for. Subjects will be given diary cards to complete for the ibrutinib taken at home. Subjects must bring the diary cards to the site on every visit so study site personnel can verify compliance.

9.1.1 Copanlisib administration:

Copanlisib is supplied as lyophilized preparation in a 6-mL injection vial. The total amount of copanlisib, BAY 80-6946, per vial is 60 mg. The solution for IV infusion is obtained after reconstitution of the lyophilisate with 0.9% sodium chloride solution. Please refer to the Pharmacy Instructions for detailed instructions for the reconstitution of the lyophilisate and for further dilution of the reconstituted solution. Study drug is administered in a normal saline solution, intravenously, over 1 h (or per MSK protocol). No intravenous glucose preparations should be administered on the days of infusion. Dosing is weekly for the first 3 weeks of a 28-day cycle (on Days 1, 8, and 15), followed by a 1-week break (i.e., no infusion on Day 22). Patients will be on 30 mg, 45 mg or 60 mg depending on their dose level.

Laboratory blood tests on day 1 of copanlisib treatment must follow the below criteria:

Table 9-1: Laboratory test criteria for Day 1 dose of subsequent cycles

Laboratory Test	Criteria for Day 1 dose (Cycle 2 and higher)
Glucose	< 160 mg/dL (fasting) or < 200 mg/dL (non-fasting)
Hemoglobin	$\geq 8 \text{ g/dL}$ ^a
ANC	$\geq 1 \times 10^9$
Platelets	$\geq 75 \times 10^9$ ^b

ANC = Absolute neutrophil count;

a: If hemoglobin is < 8 g/dL but $\geq 6 \text{ g/dL}$ on the day of planned study drug administration it is permissible to give the study drug dose as scheduled and transfuse within 48 hours after the dose, if the patient is hemodynamically stable and in opinion of investigator benefits outweigh risks. Rationale and treatment should be recorded in source document and eCRF.

b: If Platelets is $<75 \times 10^9$ but $\geq 50 \times 10^9$ on day of planned study drug administration, it is permissible to give study drug if this is related to disease.

Glucose Monitoring for copanlisib administration

Treatment – Cycle 1

Cycle 1, Day 1

The following assessments should be performed on Cycle 1, Day 1 before receiving study treatment unless otherwise specified.

- On Cycle 1 Day 1, patients should be fasting for at least 8 h prior to the pre-dose glucose measurement. Fasting glucose should be < 125 mg/dl for non-diabetic patients or <160 mg/dl for diabetic patients.
- Glucose will be measured at 0 h (pre-dose) and post dose 1 hour and 2 hours after the end of copanlisib infusion (deviation of ± 15 min is allowed). Additional measurements to be performed at the clinic as clinically indicated.

NOTE: Patients should be educated on the signs and symptoms of hyperglycemia, such as frequent urination, increased thirst, blurred vision, headaches and difficulty concentrating and must report these to the investigator or their physician immediately. If patient needs to take a meal, then glucose test should be taken prior to meal intake.

Cycle 1 Day 8, Cycle 1 Day 15, and all subsequent doses

- Fasting is not required before first glucose measurement.
 - If patient is fasting, glucose should be <160 mg/dl prior to copanlisib infusion
 - If patient is non-fasting, glucose should be <200 mg/dL prior to copanlisib infusion
- Glucose will be measured prior to and after the end of copanlisib study drug IV infusion (deviation of ± 10 min is allowed, except for the pre-dose measurement). Patients are not required to be fasting prior to pre-dose glucose measurement.

Blood pressure measurement on treatment days

Blood pressure will be measured every 5 – 10 minutes prior to each copanlisib dose (no more than 4 measurements) until there are two consecutive results $< 150/90$ mmHg. If blood pressure is $\geq 150/90$ mmHg, the investigator can consider a medical intervention or delaying the infusion of study drug. The patient should rest for 5-10 minutes before blood pressure is recorded.

On infusion days, blood pressure will be measured at 0 h (pre-dose), 30 min (mid-infusion), 60 min (end of infusion), and 1 h and 2 hours after the end of infusion

Note: a window of ± 10 min is allowed for all BP measurements

Ibrutinib administration:

Ibrutinib will be administered once daily continuously until disease progression, intolerance, or completion of 36 cycles, not exceeding 36 cycles since start of therapy whichever comes first. Patients will be instructed to take 420 mg or 560 mg depending on the treating cohort.

Ibrutinib should be administered at about the same time each day orally with 8 ounces or approximately 240 mL of water. The drug should be swallowed intact and subjects should not attempt to crush dissolve the tablets in water. If a dose is missed, the dose may be taken as soon as possible on the same day with a return to the normal schedule the following day. Extra tablets of ibrutinib should not be taken to make up for the missed dose. If a patient vomits the dose, the dose should not be retaken. On days when patients are receiving copanlisib and ibrutinib, patients should take their dose of ibrutinib in clinic just prior to the copanlisib infusion.

9.2. Definitions of dose limiting toxicity, maximum tolerated dose, and recommended phase II dose

A dose limiting toxicity (DLT) is defined as any of the following adverse events occurring within cycle 1 (28 days). A maximum tolerated dose (MTD) is defined as the highest dose studied for which the incidence of DLT is less than 33%. The recommended phase II dose (RP2D) is the dose with clinical efficacy without major toxicity.

- Any AE resulting in a dose delay of >7 consecutive days within the DLT period based on dose modifications in Table 9-6
- Non hematologic AE:
 - Hemorrhage requiring transfusion or procedural intervention, intracranial hemorrhage, intraocular hemorrhage of any grade
 - Grade 4 arterial hypertension
 - Any Grade ≥ 3 AE EXCEPT noted below
 - Grade ≥ 3 nausea, vomiting, constipation or diarrhea persisting for <48 hours
 - Grade ≥ 3 rash or skin hypersensitivity persisting for <7 days
 - <7 days of Grade ≥ 3 fatigue
 - <7 days of Grade ≥ 3 edema
 - <7 days of post infusion blood glucose >250 mg/dL despite optimal glucose management or <2 days of blood glucose >500 mg/dL despite optimal glucose management

- Grade 3 (or 4) isolated electrolyte abnormalities that resolve, with or without intervention, to Grade \leq 2 in less than 72 hours Hematologic AE
 - Any Grade 4 neutropenia lasting more than 7 consecutive days
 - Febrile neutropenia \geq Grade 3 (ANC $<1000/\text{mm}^3$ with a single temperature of $>38.3^\circ\text{C}$ or a sustained temperature of $\geq 38^\circ\text{C}$ for more than 1 hour
 - Grade 4 thrombocytopenia lasting more than 7 days or Grade 3 thrombocytopenia with evidence of \geq Grade 2 bleeding
- Any Grade 5 toxicity is considered a DLT.

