Each patient is allowed a maximum of two dose reduction of each study drug. Dose reduction of copanlisib or ibrutinib indicates treatment at the next lower dose of copanlisib or ibrutinib based on Table 9-6. If after treatment interruption, resolution of toxicity, and treatment resumption at same dose, the subject presents with the same toxicity at the same severity, then the next treatment re-

initiation must resume at the next lower dose level irrespective of duration. A patient must discontinue therapy if after therapy is resumed at a lower dose, the same toxicity recurs with the same or worse severity. Copanlisib and ibrutinib dose modification guidelines for specific toxicities are outlined in Table 9-7.

Table 9-6. Intrapatient dose reduction*

Drug	Maximum Dose Levels	Reduction Dose Level 1	Reduction Dose Level 2
Copanlisib	60 mg	45 mg	30 mg
Ibrutinib	560 mg daily	420 mg daily	280 mg daily

*Dose reduction starts from the treating dose.

Dose escalation is allowed after the DLT period for ibrutinib to the FDA approved dose levels of 560 mg. However, patients will only be allowed to escalate to this dose once the DLT evaluation period for Dose Level 1 has passed and the dose will not exceed what has been deemed the MTD in other patients. There will be no intrapatient dose escalation of copanlisib. Once a dose reduction for copanlisib of a patient has occurred, the dose level may not be re-escalated during subsequent treatment cycles.

The sections below describe dose reduction steps for patients enrolled in the expansion phase of the study. For patients in the dose expansion phase, the dose must be held per these guidelines and these dose reduction steps can be followed after cycle 1 and per discussion with the PI. Inability to meet treatment criteria will result in holding the dose. If patients have been dose reduced to dose level -1 and continue to meet dose modification criteria to reduce the dose, they will be removed from study treatment.

Table 9-7. Dose modification guidelines

Toxicity Category	Severity (CTCAE 5.0 Grade)	Dose Modifications for ibrutinib	Dose Modifications for copanlisib
HEMATOLOGIC			

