	
Level 4: > 500 mg/dL (≥ 27.8 mmol/L)
	
Dose adjustments of ibrutinib per investigator discretion
	
Immediately omit copanlisib, initiate or intensify medication with appropriate anti-diabetic treatment, re-check within 24 hours. If level improves then follow specific level recommendations.
 
If FPG is confirmed at Level 4:
 
• Administer intravenous hydration and intervention for electrolyte/ ketoacidosis/hyperosmolar disturbances as clinically appropriate• Discontinue patient from study• Instruct patient to follow dietary guidelines according to local and/or institutional standards for management of diabetes mellitus (such as those provided by the American Diabetes Association) during the study• Consider use of oral anti-hyperglycemic therapy such as metformin• Consider referral to endocrinologist for diabetic management 
For non-fasting plasma glucose >500 mg/dL (> 27.8 mmol/L) accompanied by signs/symptoms of hyperglycemia (for example, mental status changes, excessive thirst, polyuria), or presence of blood or urine

			ketones, discontinue copanlisib and following guidance for management of Level 4 fasting plasma glucose (FPG).
CARDIAC			
Arterial hypertension	Dose modify/hold copanlisib because of association with arterial hypertension. May dose modify/hold ibrutinib as clinically indicated		
	Pre-dose measurements BP \geq 150/90 mmHg	Maintain ibrutinib dose per investigator discretion	Delay copanlisib until recovery to < 150/90 mmHg Consider BP lowering medication. Dosing can proceed on the scheduled day if after at least 2 consecutive measurements BP returns to < 150/90 mmHg. If BP doesn't return to < 150/90 mmHg, delay dosing until next visit.
	During infusion: Grade 3 (\geq 160/100 mmHg)	Dose adjustments of ibrutinib per investigator discretion	Infusion can be interrupted or slowed down and administration of BP lowering therapy should be initiated. Infusion maybe resumed when BP has returned to < 150/90 mmHg at the investigator's discretion or skipped. Subsequent study drug administrations maybe reduced by 1 dose level at the investigator's discretion.

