Grade 1	CT scans with lung windows. Repeat at least every 8 weeks (+/- 1 week), (or as per local practice) until return to within normal limits.	No specific therapy is required	No change	NA
Grade 2	CT scan with lung windows. Consider pulmonary function testing includes: spirometry, DLCO, and room air O ₂ saturation at rest. Repeat at least every 8 weeks (+/- 1 week), (or as per local practice) until return to within normal limits. Consider a bronchoscopy with biopsy and / or BAL.	Symptomatic only. Consider corticosteroids if symptoms are troublesome.	Dose interruption until recovery to ≤ grade 1	Decrease dose to the next lowest dose level, minimum dose is 30mg copanlisib ^a
Grade 3	CT scan with lung windows and pulmonary function testing includes: spirometry, DLCO, and room air O ₂ saturation at rest. Repeat at least every 8 weeks (+/- 1 week), (or as per local practice) until return to within normal limits. Bronchoscopy with biopsy and / or BAL is recommended.	Consider corticosteroids if infective origin is ruled out. Taper as medically indicated.	Discontinue copanlisib	NA
Grade 4	CT scan with lung windows and required pulmonary function testing, if possible, includes: spirometry, DLCO, and room air O ₂ saturation at rest. Repeat at least every 8 weeks (+/- 1 week), (or as per local practice) until return to within normal limits. Bronchoscopy with biopsy and / or BAL is recommended if possible.	Consider corticosteroids if infective origin is ruled out. Taper as medically indicated.	Discontinue copanlisib	NA

Guidelines for the treatment of copanlisib induced arterial hypertension

No dose should be given if blood pressure is ≥ 150/90 mmHg. Antihypertensive medication may be given to control the increased blood pressure. Dosing can proceed on the scheduled day if there are at least 2 consecutive measurements <150/90 mmHg. Otherwise dosing must be delayed.

If drug-related arterial hypertension (post-dose blood pressure of CTCAE Grade 3 or \geq 160/100 mmHg) is not manageable with optimal antihypertensive treatment, the dose for the subsequent copanlisib administrations may be reduced by 1 or 2 dose levels at the investigator's discretion. Patients with a post-dose blood pressure that may have life-threatening consequences (e.g. malignant arterial hypertension, transient or permanent neurologic deficit, hypertensive crisis) must permanently discontinue the study drug. Please see table 9-7.

Treatment of blood pressure increases associated with copanlisib

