E: Post Infusion Blood Pressure Evaluation: Blood pressure (5-10min, +/- 10 min) prior to copanlisib must be <150/90mmHg for two consecutive measurements. If blood pressure prior to infusion is ≥150/90 mmHg, medical intervention or dose delay should be considered. Blood pressure post infusion should be measured at 30 min (mid-infusion), 60 min (end of infusion), 1 hour and 2 hour post infusion (+/- 10 min).
F: Radiographic assessment via PET and CT chest/abdomen/pelvis and neck CT if clinically indicated (MRI will be used for those who are unable to undergo CT scans).
G: Pretreatment archived biopsy material (10-15 x 10 microns) or an optional pretreatment core biopsy (2-3 cores). Post treatment optional core biopsy (2-3 cores).
H: Maximum 36 cycles, not exceeding 36 months of treatment
J: Exact schedule for PK testing is in Table 9-4.
K: Not required to collect if patient has begun new anti-cancer therapy within 30 days after last dose of either study drug on protocol.

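### At a pre-dose blood pressure of 150/90 mmHg or higher, the protocol makes holding copanlisib optional in two places and mandatory in three, in both phases

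*Combined protocol and SAP*

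**What the plan says.** The threshold is 150/90 mmHg throughout. The action attached to it differs.

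**Permissive wording**
- Section 9.1.1, on blood pressure on treatment days, has readings taken every 5 to 10 minutes before each dose, four at most, until two in a row are below 150/90 mmHg. If the pressure is at or above that level, "the investigator can consider a medical intervention or delaying the infusion of study drug".
- Table 10-1 footnote E, second sentence: "medical intervention or dose delay should be considered".

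**Mandatory wording**
- Section 9.8, guideline on copanlisib-induced arterial hypertension: "No dose should be given if blood pressure is ≥ 150/90 mmHg". Dosing may go ahead the same day after at least two consecutive readings below the limit. "Otherwise dosing must be delayed".
- Table 9-7, pre-dose row: "Delay copanlisib until recovery to < 150/90 mmHg", and then "If BP doesn't return to < 150/90 mmHg, delay dosing until next visit".
- Table 10-1 footnote E, first sentence: pre-infusion pressure "must be <150/90mmHg for two consecutive measurements".

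**The concern.** Section 9.1.1 is the text that staff would consult when giving the drug, and footnote E sits under the visit schedule. Both leave the hold to judgement, whereas the toxicity guidance forbids the dose. Footnote E gives both instructions in consecutive sentences.

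The main stake is patient safety. Sections 6.2 and 6.3 set no numeric blood pressure limit for entry, so the pre-dose check is the only numeric limit before an infusion. Compliance is a second stake. An infusion given at or above 150/90 mmHg is tolerable under Section 9.1.1 and a departure under Section 9.8, so the audits in Section 16.2 have no single standard for classifying it.

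**Working it through.** The plan gives no figure to reproduce here, so the check is to follow a patient through each instruction.

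**Case A: early readings are high, then two consecutive readings fall below 150/90 mmHg within the four allowed, with or without medication.** Section 9.1.1 stops measuring once it has two consecutive low readings. Section 9.8 and Table 9-7 both let dosing proceed that day. The first sentence of footnote E is satisfied. All the texts agree.

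**Case B: four readings are taken and no two consecutive ones are below 150/90 mmHg.**

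| Text | Instruction in case B | Hold required? |
|---|---|---|
| Section 9.1.1 | Intervention or delay may be considered; no outcome stated after the fourth reading | No |
| Footnote E, second sentence | Intervention or delay should be weighed | No |
| Footnote E, first sentence | Two consecutive readings below the limit are required, and were not obtained | Yes |
| Section 9.8 | Dosing must be delayed | Yes |
| Table 9-7, pre-dose row | Delay until recovery, failing that until the next visit | Yes |

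The contradiction is therefore confined to case B, which is the case the limit exists to catch.

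**Which rule was intended?** Two features point to the mandatory hold. Table 9-7 asks the investigator to consider only the blood-pressure-lowering medication; the delay itself is an instruction. Section 9.8 also provides for documented departures from its hematologic toxicity and pneumonitis guidance, but its hypertension guideline has no such provision. The permissive sentences are thus the ones to correct.

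**Which phase?** Section 9.1.1, Section 9.8 and footnote E carry no phase limit. Table 9-7 is introduced in Section 9.7 by a paragraph that applies to each patient, and the hypertension guideline in Section 9.8 refers to it again. Both the permissive and the mandatory texts therefore reach phase I and phase II.

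**How many infusions?** The documents report no rate of pre-dose readings at or above 150/90 mmHg. The roughly 42% in Section 11.8 concerns drug-related Grade 3 hypertension after infusion, which is a different quantity. No count can be derived.

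**The case against.** The strongest reply is that the passages can be read together. Section 9.1.1 first requires readings until two in a row are below the limit, and then names two responses to a high value: treat or delay. It never lists infusing anyway. Footnote E puts its mandatory criterion directly before its permissive sentence, so the discretion could be about which remedy to use. Section 9.8 and Table 9-7 then supply the outcome that Section 9.1.1 omits. Much of this stands: it is a sensible reading, and probably what most investigators would do. It is not what the words require, however. Being free to consider a delay is not a duty to delay, and a safety limit should not depend on the reader reconciling four places.

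Two stronger readings are tempting and are not supported.

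- *Phase I has no governing rule.* A reader might infer this from Section 9.7, where the paragraph that makes holds binding begins "The sections below describe dose reduction steps for patients enrolled in the expansion phase of the study". That paragraph does not rank Section 9.1.1 against Section 9.8, and its opening concerns dose reduction steps. Section 9.8, the first sentence of footnote E and the earlier reference to Table 9-7 already require the hold in phase I. The phase I headcount therefore does not measure the size of the problem.
- *Dose finding is distorted.* Holding Days 1 and 8 would put the first infusion on Day 15, a delay of 15 − 1 = 14 days. That exceeds the seven-day limit in the dose-limiting toxicity definition and leaves one of three infusions. It needs two consecutive holds in cycle 1 and the hypertension counted as an adverse event. The documents give no frequency for this, so it remains a possibility and not a finding.

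**Conclusion.** The inconsistency is real and should be fixed. At the same trigger, Section 9.1.1 and the second sentence of footnote E leave the hold to discretion, while Section 9.8, Table 9-7 and the first sentence of footnote E require it, in both phases. Read literally, the administration text permits an infusion that Section 9.8 bars.

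The consequence is one of safety wording and consistent conduct. No sample size, error rate, stopping boundary or other statistical figure changes. The number of infusions at risk is unknown and probably small if investigators read the protocol as a whole; that last judgement is an assumption, since the documents contain no data on it. The conclusion rests on taking the permissive sentences at their ordinary meaning.

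**What to change.** In Section 9.1.1 and in Table 10-1 footnote E, replace the permissive wording with: *copanlisib must not be given unless two consecutive readings are <150/90 mmHg (BP-lowering medication and repeat readings the same day are allowed); otherwise delay per Table 9-7*. State that the rule applies in both phase I and phase II. This also supplies the missing outcome when the four readings fail.

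The cost is a wording amendment, with no added visit, test or equipment. The downside is that a few infusions may be delayed.

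A separate, minor harmonisation could go into the same amendment. For Grade 3 pressure during infusion, Section 9.8 advises interrupting, whereas Table 9-7 allows interrupting or slowing. The sponsor should choose one and use it in both places.
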